#### **7.4.8 Treatment Compliance**

Study drug is not to be dispensed to subjects. Study drug will be administered by IV infusion by a qualified health care professional at the clinical site. The date, time, and volume of each dose of study drug administered to each subject must be recorded in the dispensing log for the study, as well as on the appropriate CRF.

#### **7.5 Study Procedures and Assessments**

Informed consent must be obtained prior to any Screening procedures. The Baseline (Week 0) visit must take place within 30 days of the Screening visit. Screening assessments (physical exam and safety labs) performed within 7 days prior to the first dose of study drug may be used for Baseline assessments. Subjects will be treated only after all inclusion/exclusion criteria have been confirmed. Baseline assessments must be completed within 7 days prior to first dose of study drug, unless otherwise specified. Assessments scheduled on the same day as treatment must be performed prior to the infusion.

Subjects will return to the clinic at 2-week intervals ( $\pm 3$  days) throughout the 48-week Treatment Period for study drug infusion and basic safety measures. Major assessment visits (Weeks 12, 24, 36, and 48) are scheduled at 12-week intervals ( $\pm 7$  days).

All assessments scheduled for a treatment day must be completed prior to the infusion on that day. For subjects who discontinue prior to completing the study, every reasonable effort should be made to perform the Early Termination visit procedures within 2 weeks of administration of last dose of study drug.

Following completion of the 48-week Treatment Period, subjects may participate in the Continuation Period for up to 240 weeks. Subjects will return to the clinic for UX003 administration every 2 weeks; additional assessments will be conducted at 12, 24 or 48-week intervals ( $\pm 7$  days).

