**Table 2.2: Schedule of Events Continuation Period**

Assessment	Continuation Period Weeks 50-240 c
Urinary GAG g	Every 12 weeks
Anthropometrics (including weight) h	Every 12 weeks
CGI	Every 12 weeks
Pulse oximetry	Every 12 weeks
Bayley-III	Every 48 weeks
Motor Milestone Checklist	Every 48 weeks
Echocardiogram i	Every 48 weeks
Liver and spleen ultrasound k	Every 48 weeks
Adverse events l	Every 2 weeks
Concomitant medications and therapies	Every 2 weeks
Physical examination m	Every 12 weeks
Vital signs n	Every 2 weeks
Clinical laboratory tests o	Every 24 weeks
Antibodies to rhGUS p	Every 12 weeks
Bone turnover markers	Every 24 weeks
Complement C3, C4, CH50 (subjects with IARs) q,r	As indicated
Treatment with UX003	Every 2 weeks

Abbreviations: Bayley-III = Bayley Scales of Infant Development® – Third Edition, CGI = Clinical Global Impression scale, con-meds = concomitant medications, PK = pharmacokinetics, GAG = glycosaminoglycans, ET = early termination

- a. Screening must take place within 30 days prior to Baseline Visit. Informed consent/assent must be obtained prior to any Screening procedures.
- b. Baseline assessments must be completed within 7 days prior to first dose of study drug, unless otherwise specified. Physical exams and safety labs are the only Screening assessments that, if performed within 7 days of the first dose of study drug, may be used for Baseline assessment. Baseline assessments must be performed prior to the infusion if scheduled on the same day as the Week 0 visit.

- c. Visit windows are  $\pm 3$  days during the Treatment Period. For major assessment visits (Weeks 12, 24, 36, and 48) and visits during the Continuation Period the window is  $\pm 7$  days. All assessments scheduled for a treatment day must be completed prior to the infusion on that day.
- d. Growth history for height and weight will be collected as part of medical history. Pretreatment measurements of height and weight should be collected from the records if possible to assure a pre and post treatment growth rate can be assessed. Medical history collected at the Baseline visit record any changes in medical history since Screening.
- e. Weight to determine appropriate study drug volume for the subsequent visit, and for safety; refer to Pharmacy Manual for instructions on calculating drug dosage and preparation.

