- s. If a subject discontinues study treatment or withdraws from the study, every attempt should be made to complete the early termination (ET) visit within 2 weeks of the last dose of study drug. Ultrasound, Bayley-III, and motor milestone checklist will not be performed at the ET visit if the assessment was conducted within 1 month of termination.
- t. Optional assessment can be performed at a different time-point if total blood volume at week 16 may exceed maximum allowable volume.

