## 7 INVESTIGATIONAL PLAN

### 7.1 Overall Study Design and Plan

UX003-CL203 is an open-label, multicenter, Phase 2 study to assess the safety and efficacy of UX003 in pediatric MPS 7 subjects. The study seeks to enroll approximately 15 subjects less than 5 years of age at the time of informed consent, and will attempt to include approximately 5 infants with hydrops fetalis if possible. Subjects with prior exposure to UX003 treatment under an emergency IND may also be enrolled at the discretion of the Sponsor. In the initial 48 weeks of treatment, subjects will receive UX003 via IV infusion at a dose of 4 mg/kg QOW. Subjects who complete the 48-week study may choose to continue UX003 treatment in the Continuation Period up to 240 weeks, or until the subject withdraws consent, the subject is discontinued from the study at the discretion of the Investigator or Ultragenyx, or the study is terminated. Figure 7.1.1 provides a schematic of the overall study design.

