### **7.3.3 Removal of Subjects from Therapy or Assessment**

In accordance with the Declaration of Helsinki, subjects have the right to withdraw from the study at any time for any reason. The Investigator and Ultragenyx also have the right to remove subjects from the study. Ultragenyx must be notified of all subject withdrawals as soon as possible. Ultragenyx also reserves the right to discontinue the study at any time for either clinical or administrative reasons and to discontinue participation of an individual subject or Investigator due to poor enrollment or noncompliance, as applicable.

Subjects may be removed from the study for the following reasons:

- Occurrence of an unacceptable AE
- An illness that, in the judgment of the Investigator or Ultragenyx, might place the subject at risk or invalidate the study
- At the request of the subject (or legally authorized representative), Investigator, or Ultragenyx, for administrative or other reasons
- Protocol deviation or unreliable behavior

If the reason for removal of a subject from the study is an AE, the AE and any related test or procedure results will be recorded in the source documents and transcribed onto the case report form (CRF). Each clinically significant abnormal laboratory value or other clinically meaningful abnormality should be followed until the abnormality resolves or until a decision is made that it is not likely to resolve. If such abnormalities do not return to normal within 30 days after the last dose given, their etiology should be identified and Ultragenyx should be notified. All unscheduled tests must be reported to Ultragenyx immediately.

If a subject discontinues from the study prematurely, every reasonable effort should be made to perform the Early Termination Visit procedures within 2 weeks of the last dose of study drug.

Subjects who withdraw or are removed from the study after receiving study drug may be replaced on a case-by-case basis, at the discretion of Ultragenyx.

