### **7.5.3 Drug Concentration Measurements**

The concentration of rhGUS in the blood will be measured to characterize the PK of UX003 following a single dose and multiple doses. Blood samples for PK analysis will be obtained at Weeks 0 (Baseline), 24, and 48. PK samples will be collected prior to the infusion (pre-dose), 60 minutes after start of infusion, at the end of the infusion, 30-120 minutes post infusion and 4-6 hours post infusion.

Samples may be obtained by separate venipunctures, indwelling catheters, peripherally inserted central catheter (PICC) line or by combinations of these or other suitable methods. The indwelling or PICC line should be managed as prescribed by the clinic procedures. Collection and processing instructions can be found in Laboratory Manual. The same IV line post-infusion end, may be used if the primary line fails, but extensive saline flushing of the line should occur before drawing PK.

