#### **7.5.4.9 Adverse Events**

All AEs will be recorded from the time the subject signs the informed consent until 30 days after the last dose of study drug. The determination, evaluation, reporting, and follow-up of AEs will be performed as outlined in Section 8.5. At each visit subjects will be asked about any new or ongoing AEs since the previous visit. Assessments of AEs will occur at each study visit.

Clinically significant changes from study baseline in physical examination findings, weight, vital signs, and clinical laboratory parameters, will be recorded as AEs or SAEs, if appropriate.

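### Adverse events are to be recorded for 30 days after the last dose, but no scheduled contact covers that window and the triggers for the Early Termination visit disagree (cheap improvement)

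*Protocol*

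**What the plan says.** **Recording window.** Protocol 7.5.4.9: "All AEs will be recorded from the time the subject signs the informed consent until 30 days after the last dose of study drug". Note l to the schedule tables repeats this, and 8.5.4 sets the same 30-day limit for SAEs and for deaths from any cause.

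**How events are found.** Also in 7.5.4.9: "Assessments of AEs will occur at each study visit". At each visit subjects are asked about events since the previous one.

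**Order of the day.** Note c to the schedule tables: "All assessments scheduled for a treatment day must be completed prior to the infusion on that day".

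**Week 48 is a dosing visit.** Protocol 7.5.3: "Blood samples for PK analysis will be obtained at Weeks 0 (Baseline), 24, and 48". The samples are timed before, during and after an infusion.

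**After Week 48.** Protocol 7.1: "Subjects who complete the 48-week study may choose to continue UX003 treatment". Continuation is optional.

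**Who gets an ET visit.** There are three wordings, all asking for the visit within 2 weeks of the last dose:
- Protocol 7.5: "For subjects who discontinue prior to completing the study, every reasonable effort should be made to perform the Early Termination visit procedures".
- Protocol 7.3.3: "If a subject discontinues from the study prematurely".
- Note s: "If a subject discontinues study treatment or withdraws from the study, every attempt should be made to complete the early termination (ET) visit".

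**The only other visit after a last dose.** Protocol 7.5.1 provides a termination visit within 30 days of the last dose, but only if the sponsor ends the study before Week 240.

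**The concern.** During treatment each infusion is followed about two weeks later by a visit at which events are asked about. The last infusion need not be. The protocol sets a 30-day window and relies on visits to fill it, yet schedules no visit or call at its end. For some children it arguably schedules none at all.

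Safety and tolerability is part of the primary objective, and SAP 3.4 provides no independent monitoring committee. SAP 8.8.1 puts no end date on treatment-emergent events, so an event after the last dose would enter the tables if anyone recorded it. The SAP appendix describes immune complex reactions 1 to 5 days after an infusion, with delayed onset and variable symptoms. Those are events that a family may mention only when asked.

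**Working it through.** The plan gives no figure of its own here, so the check is day arithmetic plus a comparison of the ET wordings.

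**Inputs**
- Recording window: 30 days after the last dose (Protocol 7.5.4.9, 8.5.4).
- Latest ET visit: day 14 after the last dose (Protocol 7.5, 7.3.3, note s).
- Week 48 = Day 337 and Week 240 = Day 1681 (SAP Table 7.3–1).

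**Step 1: what follows the Week 48 infusion that day.** The adverse event question comes before the infusion under note c. After it, the plan has vital signs to 60 minutes (7.5.4.4) and PK samples to 4–6 hours (7.5.3).

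**Step 2: where the window ends.**
- Last dose at Week 48: 337 + 30 = Day 367. The next scheduled visit, Week 50, is Day 50 × 7 + 1 = 351 and exists only for children who continue.
- Last dose at Week 240: 1681 + 30 = Day 1711. This assumes a dose is given at Week 240, as the two-weekly treatment row of Table 2.2 implies. Section 7.5.1 ends the trial at the last subject's Week 240 visit.

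**Step 3: days without a scheduled contact** (30 minus the day of the last contact).

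| Situation | Calculation | Uncovered days |
|---|---|---|
| ET visit on day 14 | 30 − 14 | 16 (16/30 = 53%) |
| ET visit on day 7 | 30 − 7 | 23 |
| No ET visit | 30 − 0 | 30 (100%) |
| Contact on day 30 | 30 − 30 | 0 |

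So 16 days is the smallest gap the ET visit can leave, whichever trigger applies.

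**Step 4: does a child who stops after the Week 48 infusion get an ET visit?** Section 7.1 treats the first 48 weeks as something a subject completes. Under 7.5 and 7.3.3 this child has neither left before completion nor left prematurely, so no visit is owed. Under note s the child has stopped study treatment, so a visit is owed. The same split arises at Week 240.

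**Step 5: illustration with assumed risks.** The documents give neither a 30-day event risk *q* nor the number *n* of children in the gap. With independent children, the chance that at least one has an SAE or death in 30 days is 1 − (1 − *q*)^*n*. For *n* = 1 to 3 it is 1–3% at *q* = 1% and 5–14% at *q* = 5%. For *n* = 15 it is 14%, 26%, 54% and 79% at *q* = 1%, 2%, 5% and 10%. These are chances that an event occurs, not that it goes unrecorded.

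**The case against.** The best reply is that the recording duty does not depend on a visit. Section 7.5.4.9 requires all events to day 30, and asking at visits is one means. Section 8.5.4 requires SAEs and deaths to be reported within 24 hours of the site learning of them, and SAEs to be followed to resolution or stabilization. For a child removed because of an adverse event, 7.3.3 requires follow-up of significant abnormalities and further action on those not normal by 30 days. All of this stands. What may be missed is what nobody asks about, mainly non-serious or delayed events.

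A reader might go further in four ways that the documents do not support.
- *That the ET visit is owed only to children who leave before completing.* Note s has no such condition. The defect is inconsistent wording.
- *That completion is left wholly open.* No formal definition is given, but Protocol 7.1 and 7.5 and SAP 7.3 point to two completion points, the end of the 48-week period and the end of continuation.
- *That all 15 children are exposed, so that 14–79% is the chance of losing a serious event.* That needs every child to fall in the no-contact group and every event to go unreported. Children who withdraw early are due an ET visit, and a sponsor stop before Week 240 brings a termination visit.
- *That the high mortality of hydropic infants falls in this gap.* The protocol places that risk mainly at 2–4 months and before 1 year of age. A child dosed at Week 48 has already survived 48 weeks on treatment.

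The immune complex example also has limited force: days 1 to 5 are missed only if there is no ET visit, since a visit on day 14 would ask about them. Finally, SAP 3.4 says the sponsor monitors safety continually, and the safety analysis is descriptive.

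**Conclusion.** The point holds as a cheap improvement to safety follow-up. Carried out as written, the plan leaves at least days 15–30 after the last dose without active ascertainment. Where a child is taken to have completed at Week 48 or Week 240, it can leave all 30 days.

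This rests on three things: adverse events being elicited at visits, a dose being given at the final visit (explicit at Week 48 through the PK sampling, inferred at Week 240), and no further contact being set out in a manual we have not seen. The number of children affected and the number of events missed cannot be derived from the documents. The Week 48 uGAG analysis does not depend on this.

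**What to change.** **Add one contact.** In Protocol 7.5.1 and Tables 2.1 and 2.2: *Every subject, whatever the reason for stopping, will be contacted by telephone or visit 30 (+7) days after the last dose of study drug to record AEs, SAEs and survival.* This brings the uncovered days to 0.

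**Use one ET trigger.** In 7.3.3, 7.5 and note s: *subjects who stop before the Week 48 visit or, once in the Continuation Period, before the Week 240 visit.* The 30-day contact then covers children who finish either period.

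The definition of the end of trial need not change, because the 30-day recording duty already runs past the last subject's Week 240 visit. Nor is split reporting of completion needed in the SAP.

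**Cost.** About 15 calls or visits, no extra samples, one added row or column in each schedule table, and a small protocol amendment with IRB/EC approval. Under 8.1.3, subjects' representatives would consent again if the consent form is revised.

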##### **7.5.1 Schedule of Events**

The parameters to be assessed in Study UX003-CL203, along with timing of assessments, are provided in the Schedule of Events ([Table 2.1](#) and [Table 2.2](#)). Refer to the Study Reference Manual for additional details on specific assessments. For any given study visit, if the maximum amount of blood has been taken based on Maximum Allowable Blood Volume Guidelines for any subject, some assessments are not required; see the Lab Manual for details on prioritizing blood draws.

The end of trial is defined as the last visit of the last subject undergoing evaluation in the study. As the planned duration of treatment in this study is up to 240 weeks, the end of trial is defined as the Week 240 visit of the last subject. In the event the study is terminated by the Sponsor prior to Week 240, all subjects should complete a termination visit and the date of the last termination visit of the last subject would define the end of the trial. The termination

visit should be completed within 30 days of the last dose of study drug. Efficacy assessments performed within 30 days will not be repeated at the termination visit.

## **7.5.2 Efficacy Measures**

The primary efficacy variable in this study, uGAG excretion, will provide a biochemical measure of the biological action of UX003. The primary efficacy measure will be supported by multiple secondary and tertiary variables to provide an assessment of UX003 efficacy in MPS 7 patients less than 5 years of age.

### **7.5.2.1 Primary Efficacy Measure: Urinary GAG Excretion**

Clinical evidence for the use of uGAG as a relevant primary endpoint is based on nonclinical research work over 20 years, clinical disease survey studies, and Phase 3 controlled studies in MPS 1, 2 and 6 patients using other ERTs. The results demonstrate a direct relationship between disease severity and clinical outcomes with uGAG levels. The studies also demonstrate the sensitivity of uGAG to differences in clinical effect within the therapeutic range of doses and verified the sustained long-term effects of the ERT. The overall summary of these data show that uGAG reductions above a threshold of >50% are associated with clinically meaningful changes in clinical parameters in all three MPS ERT programs.

First morning void urine will be evaluated for uGAG at the time points listed in the schedule of events ([Table 2.1](#)). Urine samples will be collected once during Screening Period and on two separate days during the Baseline Period (Week 0). Urine samples must be collected from first morning voids to assure the urine is adequately concentrated. Samples will be evaluated for uGAG concentration and normalized to urinary creatinine concentration. Refer to the Laboratory Manual for details on sample collection and processing requirements.

### **7.5.2.2 Secondary Efficacy Measures**

#### **7.5.2.2.1 Growth**

Growth will be assessed as a secondary efficacy measure to assess changes in growth velocity and comparisons to normative data matched for age and gender. Anthropometric measurements include standing height (recumbent length or sitting height as appropriate), head circumference, and weight, and will be obtained at twelve-week intervals beginning at the Baseline visit (Week 0). Every effort should be made to collect standing height. If unable to collect standing height, sitting height or length should be collected for that subject.

Growth velocity will be calculated and compared with pre-treatment growth velocity when available. Anthropometric measurements may also be compared to normative reference data matched for age and gender. Refer to the Study Reference Manual for additional details on anthropometric measurements.

#### **7.5.2.2.2 Hepatosplenomegaly**

The volume of the liver and spleen will be determined using ultrasound and compared with normal values for age and gender if available; ascites will also be assessed. Ultrasounds will be conducted at the Baseline (Week 0) and Week 12, 24, and 48 (or Early Termination) study visits. During the Continuation Period, an ultrasound of the liver and spleen will be performed annually (every 48 weeks). If an ultrasound cannot be performed, liver and spleen size may be assessed qualitatively by physical exam. Ultrasound will not be performed at the ET visit if the assessment was conducted within 1 month of termination.

#### **7.5.2.3 Tertiary Efficacy Measures**

The following tertiary efficacy variables will also be evaluated in the study. Refer to the Study Reference Manual for additional details.

##### **7.5.2.3.1 Serum and Supplementary Urinary GAG Measures**

Abnormal (pathologic) GAG in the serum will be assessed. One serum sample should be collected prior to dosing at the Baseline, Weeks 12, 24, 36, and 48 visits during the Treatment Period. . Supplementary assays for uGAG may be performed; samples will be collected as described in Section [7.5.2.1](#).

##### **7.5.2.3.2 Clinical Global Impression Scale**

The Clinical Global Impression (CGI) scale was developed for use in National Institute of Mental Health-sponsored clinical trials to provide a brief, stand-alone assessment of the clinician's view of the patient's global functioning prior to and after initiating a study medication ([Guy 1976](#)). The CGI provides an overall clinician-determined summary measure that takes into account all available information, including knowledge of the patient's history, psychosocial circumstances, symptoms, behavior, and the impact of the symptoms on the patient's ability to function. The Sponsor has developed an MPS disease-specific and age-appropriate version of the CGI (also referred to as the Physician Global Impression of Change [PGI-C] in some studies) to be used in this study.

Physicians caring for each subject will provide a global assessment of change using a seven point scale ranging from -3 (severe worsening) to +3 (significant improvement). The CGI score will be supported by reported changes relative to baseline or identification of a new finding based on a list of disease-specific abnormalities projected to respond to treatment. The CGI will be evaluated at the Baseline (Week 0) visit and at 12-week intervals throughout the Treatment Period and Continuation Period.

